- Sham electroacustimulation (control) will not have stimulation

Study Population:

Inclusion criteria:

Subjects must fulfill all of the following inclusion criteria to be eligible for participation in the study:

- 1) Patients 0-18 years of age undergoing procedures on their congenital heart defects.
Additionally, patients with coarctation of the aorta for repair will be considered as a separate group and eligible for enrollment.
- 2) Willing to provide written Assent/Consent in English.

Exclusion criteria:

Subjects will be excluded if they fulfill any of the following exclusion criteria:

- 1) Patients with skin lesion over more than 50% of acupuncture sites.
- 2) Patients in renal failure.
- 3) Patients on chronic opioid therapy.
- 4) Unwilling to provide written Assent/Consent in English.

Concomitant Treatment:

All subjects will receive a standard anesthetic of propofol, remifentanyl and dexmedetomidine at doses needed to maintain a stable BIS number and lack of movement. When possible neuromuscular blocking agents will not be used. A morphine infusion will be used for postoperative pain control based on need. Those allergic to morphine will receive a substitute opiate by continuous infusion.

Study Procedures:

Screening:

Review of consent form- Subjects that provide written assent/consent and meet all inclusion and no exclusion criteria will be included into the study. Subjects may withdraw consent to participate at any time. Participation in the study is voluntary. Adverse events will be recorded after informed assent/consent obtained.

Surgery: Treatment/Sham

Eligible subjects will undergo blood sampling (3.5cc) and urine sample (0.5-2cc) will be obtained prior to stimulation/sham.

All subjects will have electroacustimulation pads applied at four points bilaterally: pericardial 4 (PC 4), pericardial 6 (PC 6), large intestine 4 (LI 4) and stomach 36 (ST 36). No needles will be used. ([Appendix A; 1](#))

Subjects will be randomized. Randomization will be done using block randomization with block sizes between 4 and 8. The sham procedure will use the identical set up as the treatment group, but those participants in the sham group will not receive the electro-stimulation. Stimulation/sham will begin as soon as possible after induction of anesthesia and obtaining baseline laboratory samples of urine and blood.

Group 1: Receive electroacustimulation (treatment) frequency will be at 2Hz and 100 Hz the amplitude will be 1000mA.

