Group 2: Receive sham electroacustimulation (control) will not have stimulation. Subjects will undergo procedures on their congenital heart defects.

Blind:

The anesthesia provider will be blinded as to whether the electroacustimulation device is actually turned on or not. The research coordinator will hold the blind. The electroacustimulation machine will be placed in an opaque bag to secure the blind. The current is below the threshold to stimulate the muscle so that no movement will be visible. It is also below the sensory threshold so that it will not produce any discomfort in the subjects.

Stimulation/Sham will be continued until the patient is ready for transport to the PICU.

Post-Operative: PICU

Stimulation/Sham will be discontinued.

PICU care givers will be blinded as to which group the patients were randomized.

Subject comfort will be assessed using age appropriate West Virginia University Hospital approved nurse guide pain scoring based on Universal Pain Assessment Tool or the Neonatal/Infant Pain Scale (NIPS) will be recorded in the electronic medical record (EMR) every 6 hours for 48 hours.

The amount of opiate infused, Nausea, Vomiting, and urine output will be assessed every 6 hours for the first 48 hours and recorded in the EMR.

Research blood samples for troponin I will be obtained at 6 hours post surgery. Total amount of 7cc of blood will be

obtained for this study. WVUH lab will process samples.

Research urine samples (.05-2cc) will be collected at 6, 12, 24, and 48 hours after bypass. The urine samples will be stored in a -80 degree freezer and analyzed by ELISA testing at the end of the study for Superoxide dismutase, Neutrophil gelatinase – associated lipocalin (NGAL), WNT4.

AKIN criteria will be used to evaluate AKI every 6 hours. Inotropic score will be recorded every 6 hours.

Daily chest x-ray will be used to assess pulmonary status.

The AKIN criteria, inotropic scores, chest x-ray and creatinine levels, (used for AKIN), are standard of care measurements and the data will be collected for this research project.

An Electrostimulation Documentation Guide has been developed for the staffing. (Appendix A2)

Tool/Instruments to be used in data collection:

Tools and instruments for data collection: secured Excel data base; Neonatal/Infant Pain Scale (NIPS); AKIN stage; Inotropic Scores; RACHS categories (Appendix A3-6).

Variables:

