Detailed descriptions of the variables are given in Appendix B. The information collected for each patient will include the following variables. *Outcomes:* Pain score; inotropic score; Narcotic use; renal laboratory values: creatinine, neutrophil gelatinase-associated lipocalin (NGAL), WNT4, AKIN score; superoxide dismutase; indicator for pneumonia; time-to-extubation (intubation time, extubation time); length of pediatric intensive care unit (PICU) stay (arrival time, discharge time). *Other variables:* Age, sex, cardiac defect, cyanosis, RACHS score, cardiopulmonary bypass time (CPB), cross clamp time and surgery start and end time, occurrence of nausea, vomiting event, urine output, number of lobes with atelectasis.

Analytic methodology

Randomization: Eligible participants will be randomized to the acupuncture treatment or control group using a randomly varying block randomization method to ensure equal distribution among treatment groups.²² The project statistician, who will have no contact with the participants or any of the personnel assessing the patients, will generate a randomized assignment master list and provide this information only the study personnel who will be setting up the acupuncture device. Each participant will be assigned a unique number that will follow the patient through the study. The study number and participant's name will be retained on a secure electronic database; this information will be linked to the randomization assignment to create a crosswalk file. It will be stored in a separate password-protected database. At the end of the study, the cross-walk file will be used to link the patient data and treatment allocation.

Sample size:

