Appendix B: Variable descriptions.

Variable	Description	Measurement times	Measurement scale
Outcomes			
Pain score	Age appropriate WVUH approved Nurse guided pain scoring. The pain scale score will be recorded in the electronic medical record.	Every 2 hours for 48 hours	Tool: NIPS score, FLACC score or Visual analog scale Scale: 0-10; 0=none, 10=worst pain
Inotropic score	IS or VIS 1 st 24 hours IS or VIS 24-48 hours	Every 6 hours for the first 48 hours of observation	Group 1-5
Narcotic use	Opiate use will be its own variable as well as a surrogate for pain as comfort will be maintained at a score less than 40% of the max possible score for the pain scoring system used.	Every 2 hours for 48 hours	mcg/kg/hr
Creatinine/Urine	Assessment of AKI-renal complication	Baseline, 6, 12, 24, and 48 hrs post CPB	Creatinine mg/dl Urine ml/kg/hr
Neutrophil gelatinase-associated lipocalin (NGAL)	Renal biomarker-urine sample collected and frozen-renal complication	Baseline, 6, 12, 24, and 48 hrs post CPB	ELIZA
WNT4	Renal Biomarker-urine sample collected and frozen-renal complication	Baseline, 6, 12, 24, and 48 hrs post CPB	ELIZA
AKIN score	Acute kidney injury (AKI)-renal complication	Every 6 hours for the first 48 hours of observation (EMR)	Stage 1-3
Superoxide dismutase	Renal Biomarker-urine sample collected and frozen-cardiac injury-complication	Baseline, 6, 12, 24, and 48 hrs post CPB	ELIZA
Pneumonia	complication	Daily (Chest x-ray)	Indicator: 0=No, 1=Yes
Intubation time	The date and time of intubation as part of surgery prep.	Obtained from patient's EMR	Date and time
Extubation time	The date and time of extubation as part of surgery prep.	Obtained from patient's EMR	Date and time
PICU arrival	The date and time of arrival in the PICU	Obtained from patient's EMR	Date and time
PICU discharge	The date and time of discharge from the PICU	Obtained from patient's EMR	Date and time
Other variables			
Age	Age of the patient	Baseline	In days
Sex	Sex of the patient	Baseline	Indicator: 0=Male, 1=Female
Cardiac defect	Type of CD	Baseline	Diagnosis

Cyanosis	Blueness of skin- based on room air oxygen level less than 90% sat-guide for opiate amount-complication	Baseline	1=yes 2=no
RACHS score	Randomization Guide	Baseline	Categorical: 1 through 6
CPB start time/ Aortic clamp time	Cardiopulmonary bypass (CPB) start time/ Placement of aortic clamp	Obtained from patient's EMR	Date and time

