CPB end time/Removal of aortic clamp	Cardiopulmonary bypass (CPB) end time/ removal of aortic clamp	Obtained from patient's EMR	Date and time
Surgery start time	Surgery start time	Obtained from patient's EMR	Date and time
Surgery stop time	Surgery stop time	Obtained from patient's EMR	Date and time
Nausea	Occurrence of nausea within a 6 hour period	Every 6 hours for the first 48 hours of observation (EMR)	Indicator: 0=No, 1=Yes
Vomiting	Number of episodes in a 6 hour period	Every 6 hours for the first 48 hours of observation (EMR)	Count of occurrences
Urine output	AKI	Every 6 hours for the first 48 hours of observation (EMR)	ml/kg/hr
Atelectasis	Graded by number of lobes with atelectasis.	Daily (Chest x-ray)	Count of the number of lobes

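### Time-to-extubation is clocked from intubation, so it includes the operation and has no usable start time for a child already intubated; a post-operative clock is available at almost no cost.

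*Combined protocol and SAP*

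**What the plan says.** The Variables section lists "time-to-extubation (intubation time, extubation time") among the outcomes. Appendix B gives the two components: "The date and time of intubation as part of surgery prep" for the start and "The date and time of extubation as part of surgery prep" for the end. Both come from the electronic record.

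The times needed for a post-operative clock are also collected, but not as part of this outcome. The Variables section puts "cardiopulmonary bypass time (CPB), cross clamp time and surgery start and end time" among the other variables, and Appendix B has rows for "Surgery stop time" and for PICU arrival ("The date and time of arrival in the PICU"). The plan's other duration outcome, PICU stay, runs from PICU arrival to PICU discharge and so begins after surgery.

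On the timing of treatment, Study Procedures says "Stimulation/sham will begin as soon as possible after induction of anesthesia and obtaining baseline laboratory samples of urine and blood", and the Blind section says "Stimulation/Sham will be continued until the patient is ready for transport to the PICU".

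Patients are 0 to 18 years old, with lesions in RACHS categories 1 to 6 (Appendix A.6). Ventilation before surgery is not an exclusion criterion.

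**The concern.** The Background cites shorter ventilation times as one benefit seen in the earlier pediatric trial. The effect of interest is therefore how long a child stays on the ventilator after the operation. An interval that starts at intubation adds the operation to that quantity. In a population running from secundum ASD closure to the Norwood operation, operating length varies with the lesion, and this variation is added to the outcome in both arms.

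Two wording problems add to this. A child intubated before coming to the operating room has no intubation belonging to surgical preparation, so the person abstracting the record must enter an earlier time, substitute another, or leave a blank, and the plan does not say which. The extubation row, read literally, describes an event before surgery, which cannot be what is meant.

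At stake are the precision of the comparison, the size of any percentage reduction reported, and consistent handling of the children already intubated.

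**Working it through.** **The plan's own figure.** The only power calculation concerns morphine-equivalent dose: 0.71 against 0.57 mg/kg, SDs 0.3 and 0.2, two-sided alpha 0.05, power 80%. With difference 0.14 and average variance (0.09 + 0.04)/2 = 0.065, n per arm = 2 × (1.960 + 0.842)² × 0.065 / 0.14² ≈ 52.1, or 53. Welch power is 79.9% at 53 and 80.6% at 54, so 54 per arm (108 in total) reproduces. It says nothing about time-to-extubation, for which the plan gives no SD, effect or power. Everything below except the 54 per arm is therefore an assumption, shown over a range.

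**Effect on the estimate.** Write T = V + O, with V post-operative ventilation and O the time from intubation to end of surgery. If treatment does not alter O, the mean difference in T equals that in V: no bias. The ratio is diluted. With a control median of 8 h, a 35% reduction and a 5 h operation, the medians are roughly:
- post-operative clock: 8 h against 8 × 0.65 = 5.2 h, ratio 0.65
- intubation clock: 13 h against 10.2 h, ratio 10.2/13 = 0.78, so 35% shows as about 21%

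The absolute difference is 2.8 h on both clocks.

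**Effect on precision, hours scale.** SD(T) = √(sV² + sO² + 2ρ·sV·sO). Choose the difference that gives 80% power on V at 54 per arm: δ = 2.802 × sV × √(2/54). For sV = 4 h, δ = 2.16 h. With sO = 2 h and ρ = 0, SD(T) = √20 = 4.47 h, and power = Φ(2.16/(4.47 × 0.1925) − 1.96) ≈ 71%. Likewise, with sO = 2 h throughout:

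| SD of V | ρ = 0 | ρ = 0.5 |
|---|---|---|
| 4 h | 70.7% | 56.3% |
| 8 h | 77.6% | 68.6% |
| 24 h | 79.7% | 76.5% |

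**Effect on precision, log scale, by simulation.** 54 per arm, log-normal V (median 8 h, log-SD 0.9, 35% reduction), normal O (mean 5 h), Welch t-test on logs. The post-operative clock has about 69% power. The intubation clock has:
- about 64% with operating-time SD 1.25 h and no correlation
- about 57% with SD 1.25 h, and 52% with SD 2 h, when O correlates 0.5 with log V
- about the same as the post-operative clock if median V is 24 h (69.7% against 70.3%)

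Repeat runs moved these figures by one or two points.

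**Children already intubated.** Suppose 5% or 10% were ventilated 1 to 7 days before surgery and the site entered those earlier times. Power on the intubation clock is then about 41% or 31% by log t-test, about 51% or 41% after a Box-Cox transformation, and 56% or 48% by Mann-Whitney. The Mann-Whitney figure on the post-operative clock is about 67%. The documents give neither the rate nor the data-entry practice.

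**Extubation in the operating room.** A post-operative clock gives values at or near zero for these children. If 20% are so extubated and operating time is uncorrelated with ventilation, the log t-test has about 61% power on the post-operative clock against 63% on the intubation clock. The gain is erased, and an exact zero has no logarithm.

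**The case against.** The strongest reply is that little is lost. Without correlation or earlier ventilation the drop is about five points, and it vanishes if ventilation is long. The SAP provides transformation for skewed data, a rank test when distributional assumptions fail, and adjusted models with RACHS at least considered; RACHS would absorb part of the lesion-driven variation. The trial calls itself a pilot, this outcome is outside the stated objectives, and post-operative ventilation can be derived later from times already collected. All of this stands and limits the severity. It does not make the definition right. Operating time is not a named covariate, RACHS adjustment is only to be assessed for relevance, and choosing the clock after seeing allocation would be post hoc.

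Two stronger readings are tempting. A reader might infer that the outcome counts any ventilation before surgery. Appendix B points the other way, since it ties the start to intubation for the operation; earlier ventilation enters only if a site departs from that wording, and the documented gap is the missing rule. A reader might also infer that the definition conceals a treatment effect. It does not: the expected mean difference is unchanged.

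Nor do the documents establish that stimulation cannot affect operating time. It runs during the operation, so only the time before it starts is strictly out of reach. That it leaves operating length alone is a reasonable assumption, and no more than that.

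**Conclusion.** The point holds, as a minor one. The outcome as written contains the operation, has no start rule for children already intubated, and carries a description error in the extubation row. The consequence is imprecision and a diluted ratio, without bias in the mean difference. Under the stated assumptions the power loss runs from essentially none (24 h median) through about 5 points (8 h median, no correlation) to about 12-17 points (correlation 0.5, operating-time SD 1.25-2 h). The falls to 41% or 31% depend on a rate of earlier ventilation and a data-entry practice that the documents do not give, so they should be read as a reason to write the rule and not as an expected loss. The outcome appears in neither the primary objective nor the numbered secondary objectives, and the sample size does not rest on it.

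**What to change.** In the Variables section and Appendix B:

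1. Define the outcome as duration of post-operative ventilation, equal to extubation time minus surgery stop time, for every child, including those already intubated before surgery.
2. Set the value to zero for extubation in the operating room, and compare arms with the Mann-Whitney test that the SAP already lists. The rank test copes with zeros; it does not guarantee a gain in power when there are many of them.
3. State how reintubation and death before extubation are handled. Do this before unblinding, that is, before the cross-walk file links allocation to patient data.
4. Keep intubation time as a descriptive variable only.
5. Correct the description in the extubation row.

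No new data are needed, since both times already come from the electronic record. The cost is a little more analysis wording. PICU arrival would also be a defensible start, but one start must be fixed in advance; surgery stop matches the aim of excluding only the operation.

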A special consideration during cardiac surgery is that organ blood flow is also often affected by non-pulsatile flow or hypotension. Lele et al., in a controlled hypotension model in dogs, found that EA helped maintain better blood flow to the stomach and kidney, resulting in reduced apoptosis in those organs. Further, the apoptosis that was observed in the control animals' brains did not occur in the animals receiving EA. Points used were large intestine (LI)-4, ST-36 spleen (SP)- 6 and LI-11 stimulated bilaterally at 2 Hz with 3-5 mA.¹⁴

Research Plan:

This study will help to identify whether electroacustimulation is a beneficial anesthesia adjunct in children undergoing procedures on their congenital heart defects.

Electroacustimulation is a technique with minimal risks, which enhances the body's innate abilities to deal with the stresses and pain of surgery. Our goal is to optimize care for those patients with congenital heart disease by increasing *comfort* and *reducing complications*. This study will examine comfort using age appropriate pain scoring systems. The complications this study will focus on are myocardial injury which will be assessed by measuring Troponin levels, and renal injury assessed using AKIN criteria

Treatment Groups:

Subjects will be randomized. Randomization will be done using block randomization with block sizes between 4 and 8. The sham procedure will use the identical set up as the treatment group, but those participants in the sham group will not receive the electro-stimulation.

Group 1: Will have electrodes placed at Pericardial 4 and 6, Large Intestine 4, and Stomach 36 and receive electroacustimulation (treatment) frequency will be at 2Hz and 100 Hz the amplitude will be 1000mA.

Group 2: Will have electrodes placed at Pericardial 4 and 6, Large Intestine 4, and Stomach 36 and receive sham electroacustimulation (control) will not have stimulation.

Duration of Treatment:

The duration of treatment (stimulation or sham) for subjects will be length of surgical procedures on their congenital heart defects. Patients will be followed for 6 hours to collect data on myocardial injury and 48 hours to collect data on pain, and renal injury.

Objectives:

Primary Objective:

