The primary objective of this study is to identify whether electroacustimulation is a beneficial anesthesia adjunct in children undergoing procedures on their congenital heart defects. Does it decrease myocardial injury and or need for myocardial support. Differences between the groups Troponin I levels pre-operative and six hours postoperative will be evaluated.

Secondary Objectives:

1) Evaluate the incidence discomfort in the post- operative period.

To evaluate the incidence and severity of pain assessed by using age appropriate West Virginia University Hospital approved nurse guided pain scoring the Neonatal/Infant Pain Scale (NIPS) (children age birth to 2 months) FLACC (2 months to 7 years or unable to communicate, or VAS(age 8-18) every 2 hours for 48 hours post procedure.

2) Determine the incidence of Acute kidney injury (AKI) between these two treatment groups. Acute Kidney Injury will be evaluated by AKIN criteria. Creatinine and urines will be measured at 6, 12, 24 and 48 hours after bypass.

Need for post-operative myocardial support:

To assess the need for myocardial support an inotropic score will be used and compared between the two groups. The Inotropic score will be evaluated every 6 hours for 48 hour between the 2 groups

Study Design:

This is a single site, randomized, blinded, sham controlled, parallel group study to identify whether electroacustimulation is a beneficial anesthesia adjunct in children undergoing procedures on their congenital heart defects.

Study subjects age's birth to eighteen years, undergoing cardiac surgery for their congenital heart lesions will be considered for entrance into the study. The randomized subjects will receive either electrostimulation or sham during their surgery for CHD. Subjects are expected to remain in the hospital 48 hours post procedure. Standard of care blood samples will be obtained pre-operative and post-operative. The only study specific blood sample will be Troponin I levels which will be obtained presurgically after the lines have been placed and a 6 hours post bypass/aortic clamp removal. Urine samples will be obtained pre-surgically after placement of the Foley and every 6 hours post bypass for 48 hours while the Foley catheter is still in place .

Number of Subjects planned:

Approximately 108 patients, over the two years, with randomization of 54 allocated to each group.

- Electroacustimulation (treatment) frequency will be at 2Hz and 100 Hz the amplitude will be 1000mA.

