Predicated on the primary aim, the sample size for this pilot study we used a two-sided two-sample t-test with unequal variance t-test with an alpha level of 0.05 and power of 80%. A morphine equivalent dose of 0.71 mg/kg was used for the control group and 0.57 mg/kg for the acupuncture group. This represents a conservative 20% change between the control and acupuncture group. The standard deviation of the control group was estimated to be 0.3 mg/kg for the control group and 0.2 for the experimental group. **The total estimated sample size is 108 patients, over the two years, with 54 allocated to each group.** Historically, we would have had a potential enrollment and retention of approximately 74 patients per year accounting for a 25% non-consent rate and a 2% drop-out rate. This project is well powered for statistical significance and feasibility for a 2-year study.

Data collection:

The data will be retrieved from the EMR and imported or entered into a secured EXCEL database.

Statistical analysis plan:

For all aims, univariate statistics (e.g. mean, median, standard deviation, min, max and skew) will be used to describe the collected data. Parametric approaches (e.g. t-test, Pearson's correlation, and chi-squared test) will be used when the data satisfy the required statistical assumptions; they will be used to compare the demographic and clinical characteristics between treatment and control. If the distributional assumptions are untenable, then the Mann-Whitney test, Spearman

correlation, and Fisher's exact test will be used. We will use the Box-Cox or the exponential transformation when the absolute value of skew is greater than 0.4.

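### The sample size and its 80% power are credited to the primary aim but computed on opioid dose; the measure named under the primary objective, troponin I, has no stated power

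*Combined protocol and SAP*

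**What the plan says.** **Objectives.** The Primary Objective starts broadly, with whether stimulation is a useful adjunct to anesthesia, and then becomes specific: "Does it decrease myocardial injury and or need for myocardial support". The measure follows: "Differences between the groups Troponin I levels pre-operative and six hours postoperative will be evaluated". The Research Plan says the same, describing "myocardial injury which will be assessed by measuring Troponin levels". The numbered secondary objectives are pain and acute kidney injury. An unnumbered paragraph after them covers myocardial support: "To assess the need for myocardial support an inotropic score will be used and compared between the two groups". No objective names opioid dose.

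**Sample size.** The calculation is introduced with "Predicated on the primary aim, the sample size for this pilot study we used a two-sided two-sample t-test with unequal variance t-test", at alpha 0.05 and 80% power. Its inputs are opioid figures: "A morphine equivalent dose of 0.71 mg/kg was used for the control group and 0.57 mg/kg for the acupuncture group", with SDs of 0.3 and 0.2. The result is 108 patients, 54 per group. The section also forecasts enrolment, "accounting for a 25% non-consent rate and a 2% drop-out rate", and concludes: "This project is well powered for statistical significance and feasibility for a 2-year study".

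**Outcome lists and analysis.** The Variables section and Appendix B both list narcotic use and omit troponin I. Appendix B describes narcotic use as an outcome in its own right and as a surrogate for pain. The Statistical analysis plan names no primary endpoint. Its overall group comparison is the change from baseline to 48 hours, whereas Duration of Treatment ends the collection of myocardial injury data at 6 hours.

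**The concern.** The document assigns a stated power to an aim for which it was not calculated. A reader of the Sample size section would conclude that the trial has 80% power for its primary question. A reader of the Primary Objective would conclude that the question concerns troponin I. Both cannot be right.

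Two things are at stake. First, the documents do not say consistently which result decides the trial. Several outcomes are to be tested at 0.05, so an endpoint left open can be settled after the data are seen. Second, if troponin I is the deciding result and turns out non-significant, nothing in the plan says what size of difference the trial could have detected.

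**Working it through.** **1. Reproduce the plan's figure (opioid dose).** Inputs from Sample size: difference 0.71 − 0.57 = 0.14 mg/kg (0.14/0.71 = 19.7%, the stated 20%); SDs 0.3 and 0.2; two-sided alpha 0.05; unequal-variance t-test.

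- Normal approximation: n per arm = (1.960 + 0.842)² × (0.3² + 0.2²) / 0.14² = 7.849 × 0.13 / 0.0196 = 52.06, so 53.
- Welch t-test at n = 54: standard error = √(0.13/54) = 0.0491; non-centrality = 0.14/0.0491 = 2.85; Satterthwaite df = 53 × 0.13² / (0.09² + 0.04²) = 92.3; power from the non-central t = **80.6%**.
- At n = 53 the same calculation gives 79.9%, so 54 is the smallest n per arm that reaches 80%.

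The stated 108 is therefore exactly right for opioid dose. If the 2% drop-out is taken out of the 108, 108 × 0.98 = 105.8, about 53 per arm and 79.9% power. That loss is negligible.

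**2. Standardise the opioid effect.** Root-mean-square SD = √(0.13/2) = 0.255, so the effect is 0.14/0.255 = 0.549 SD.

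**3. Troponin I.** The documents give no mean, difference or SD. The differences below are assumptions, shown as a range. Method: two-sample t-test, two-sided alpha 0.05, equal SDs, complete data, no multiplicity adjustment, 54 per arm, non-centrality = d × √(54/2), df = 106.

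| Assumed difference (SD) | Power |
|---|---|
| 0.2 | 18% |
| 0.3 | 34% |
| 0.4 | 54% |
| 0.5 | 73% |
| 0.6 | 87% |
| 0.8 | 98% |

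Power is 79.4% at 0.54 SD and reaches 80% at 0.544 SD (0.549 SD with 53 per arm). A rounded statement should therefore say 0.55 SD. With the Mann-Whitney fallback that the Statistical analysis plan allows, and normal data, the threshold is about 0.544/√(3/π) = 0.557 SD.

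**4. If two endpoints were primary.** With a Bonferroni split to alpha 0.025, opioid-dose power at 54 per arm falls to 71.7%, and the 80% threshold for a t-test on another continuous outcome rises to 0.600 SD.

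**5. Does the main analysis fit either candidate?** A 48-hour change score cannot be formed for a marker drawn only before surgery and at 6 hours. Nor does a change from baseline suit a cumulative opioid total, which is what a dose in mg/kg implies. The Sample size section gives no period for that total. Appendix B records opioid use in mcg/kg/hr every 2 hours, while the Post-Operative section records the amount every 6 hours.

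**The case against.** The strongest reply is that the primary endpoint is not really in dispute. Only one section is headed as the primary objective, troponin I is the only measure it names, and nothing labels opioid dose as primary. The outcome lists designate no primary endpoint, so omitting troponin I from them creates no rival. This largely stands. It narrows the defect to a sample size that does not rest on the stated primary measure, but it leaves the false attribution in the Sample size section in place.

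Opioid dose is also not foreign to the objectives: Appendix B ties it to pain, which is a secondary objective. That is fair, but it makes opioid dose a measure of a secondary objective, not of the primary aim.

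The text calls this a pilot study, and a pilot may be sized on a convenient outcome. It may, if it says so. Here the text claims power for the primary aim, and the analysis plan sets formal tests at 0.05. That plan does provide Bonferroni or Scheffe adjustment when appropriate, so a multiplicity rule exists, though it does not say which endpoints it covers.

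A reader might also infer that troponin I will not be collected. The documents do not support that: Study Design schedules it before surgery and at 6 hours, and the Post-Operative section repeats the 6-hour draw. The gap is in the outcome lists.

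**Conclusion.** The point holds as an attribution error in the current text. The 80% power and the closing claim of adequate power belong to morphine equivalent dose, for which 54 per arm gives 80.6%. They do not belong to troponin I, the only measure named under the Primary Objective.

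A reader might go further and conclude that the trial is underpowered for its primary endpoint, or that 108 is too small. The documents do not support either conclusion. Without a troponin I difference and SD, power could lie anywhere from 18% to 98% over assumed effects of 0.2 to 0.8 SD. It is undetermined. The threshold of about 0.55 SD rests on a t-test, equal SDs, complete data and alpha 0.05. It is a property of the sample size and says nothing about what difference to expect. It does not carry over to the inotropic score in its grouped form.

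This should be corrected before unblinding, because the plan otherwise claims power for a question it did not calculate and leaves the deciding result open.

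**What to change.** Keep 108 patients.

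1. **Name one primary endpoint before unblinding** and align the Primary Objective, Variables, Sample size, Statistical analysis plan and Appendix B with it. State whether the inotropic score is primary or secondary, and in which form: the numeric IS/VIS of the scoring appendix or the Group 1-5 scale of Appendix B. If more than one endpoint is primary, say how the Bonferroni adjustment applies, noting that opioid-dose power is then about 72% at alpha 0.025.

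2. **If troponin I is primary,** remove the attribution to the primary aim and the unqualified closing claim from Sample size. Suggested wording: *The 80% power applies to morphine equivalent dose. For troponin I, 54 per arm gives at least 80% power only for true between-group differences of about 0.55 SD or larger on the scale analysed (two-sided alpha 0.05, t-test, equal SDs, complete data). This is a sensitivity statement.* If a troponin I difference and SD are available, state them and the resulting power. Add troponin I to both outcome lists, and specify in the Statistical analysis plan how the pre-operative and 6-hour samples are compared.

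3. **If opioid dose is primary,** say so in the Primary Objective, state the period over which the mg/kg total is counted, reconcile the 2-hour and 6-hour recording intervals, and replace the change-from-baseline rule for this outcome with a between-arm comparison of the total. The 80% statement then stands.

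The cost is a wording amendment with no extra patients. Under option 2 the power statement becomes conditional and less favourable, and the sponsor may need to look for troponin I data. Under option 3 the myocardial question becomes secondary.
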